Diabetes is a very common comorbidity in hospitalized patients. Patients with diabetes are highly likely to be hospitalized, with insulin use increasing this likelihood (1). It is estimated that up to 38% of patients in the hospital have diabetes or hyperglycemia, and likely many more have pre diabetes (2). Diabetes is associated with worse hospital outcomes including increased risk for falls, infections and readmissions. The hospital stay represents an opportunity to intervene and optimize diabetes management. Patients at our hospital also have access to specialized services including endocrinologists and certified diabetes educators. However, diabetes is a complex disease and is common for patients to feel overwhelmed with the burden of therapy. Continuous glucose monitors (GCMs) are commercially FDA approved devices for single-patient use that can measure interstitial glucose every 5 minutes. They vary slightly in the number of wear days, display and need of calibrations. Studies have shown that CGM use improves diabetes control and decrease episodes of hypoglycemia (3-5). One barrier for the effectiveness is uptake, they are not prescribed enough by primary care providers, another significant barrier has been cost. The overall goal of this current study is to assess the feasibility of initiating CGM in patients with diabetes at discharge. This strategy has the potential to overcome delay in accessing the technology and control cost.

One study looked at the feasibility of use in older patients with diabetes and dementia in the outpatient setting. In this study, of 17 people consented and 12 completed the study. Patient and caregivers reported that the device was nonintrusive and responded positively about recommending the device (6). Another study in the outpatient setting found that a total of 22 participants (48.9%) completed the study using the minimum number of 3 FreeStyle Libre sensors with 11 of the participants requiring extra sensors due to a faulty or misplaced sensor (7). One study using a 4 month Telehealth outpatient model utilizing CGM, showed 92% (55/60) completed the 4-month intervention, and 78.2% (43/55) met the criteria of follow-up CGM sensor-wear periods >90 days from baseline. This study showed improved time in range and a decrease in A1C by 1.6% (8).

B Study Objectives

B1 Primary Aim

To determine the feasibility of initiating a continuous glucose monitoring in patients with diabetes at hospital discharge. We hypothesize that starting and continuing to use a CGM at this critical time is feasible. Feasibility is defined as at least 20% of patients with diabetes referred for diabetes education meet inclusion criteria to participate and 75% agree to

participate. From those who participate, at least 50% continue using the CGM at 3 months.

B2 Secondary Aims

1. To characterize the barriers to continuing CGM use after discharge. We will systematically characterize the reasons for discontinuations (issues with wearing device, use, costs, getting refills, etc.)
2. To assess the effect of CGM initiation at hospital discharge on diabetes outcomes: Time in range, health utilization (clinic visits, ED visits, hospitalization), self-efficacy.

C Study Design

C1 Overview or Design Summary

This study will be an interventional, single-arm, open-label, prospective design.

C2 Subject Selection and Withdrawal

One hundred eligible adult patients will be recruited to the study.

2.a Inclusion Criteria

1. 18 years of age or older
2. Have diabetes (type 1 diabetes mellitus, type 2 diabetes mellitus, cystic fibrosis related diabetes mellitus)
3. Hemoglobin A1c greater than or equal to 8.0% or history of hypoglycemia unawareness
4. Able and willing to sign informed consent form
5. Have a valid telephone number
6. Willing to purchase FreeStyle Libre 2 CGM sensors out of pocket after discharge from hospital

2.b Exclusion Criteria

1. Unable to sign informed consent form
2. Have altered mental status
3. Unable to manage diabetes independently at home
4. Have utilized CGM in the past
5. Pregnancy
6. New steroid-induced hyperglycemia
7. Unwilling to participate in the study
8. Have kidney disease requiring hemodialysis
9. Taking high doses of vitamin C daily (greater than 500 mg every day)

2.c Subject Recruitment Plans and Consent Process

The study team will identify potential participants from patients referred to the diabetes service or diabetes education service. Once a participant is identified, one of the study team members will approach the patient in their private hospital room, review the study and provide them with a written informed consent form to review. The study team will follow up 1-2 days later or prior to discharge to determine if the patient is interested in participating. If the patient is interested, the study team will review the informed consent form with them, answer all study related questions and obtain written informed consent. If a patient is not interested in the study, the study team will not coerce them into participating; participation is completely voluntary.

2.d. Risks and Benefits

Participants may or may not benefit from participating in the study. Benefits of participating in the study may include the following:

1. Improved understanding of diabetes
2. Improved ability to manage diabetes
3. Discover glucose patterns previously unaware of.

Potential risks of participating in the study include the following:

1. Improperly treated diabetes risks may include: hypoglycemia, hyperglycemia, or ketoacidosis.
2. CGM sensor insertion risks may include: feeling like insulin injection; tenderness at the sensor site.
3. Pain, redness, swelling, minor infection and minor bleeding at the sensor insertion site.
4. Redness may occur where the device adhesive pads are placed.
5. Allergic reaction to one of more parts of the sensor.
6. Skin may blister or peal at the site of the sensor.
7. Sensor or insertion needle may break.
8. Fingerstick testing risks may include: finger feel sore, tender or may bleed.
9. Questionnaire risks may include: some questions may cause the participant to feel uncomfortable.

2.e. Early Withdrawal of Subjects

Participants may be withdrawn if certain situations arise:

1. Participant does not follow study instructions
2. Change in participant's medical condition (i.e., pregnancy, worsening clinical condition)
3. The study team or government agencies stop the study
4. In the opinion of the study team, there is no value in participant continuing the study.

5. If new information becomes available or harmful unexpected reactions are experienced by participants in the study.

C3 Study Device

3.a Description

FreeStyle Libre 2 Continuous Glucose Monitoring System manufactured by Abbott

D Study Procedures

D1 Screening for Eligibility

The study team will identify potential participants from patients referred to the diabetes service or diabetes education service. Once a potential patient has been identified, one of the study team members will review the inclusion/exclusion criteria to determine if the patient is eligible to participate.

D2 Schedule of Measurements

VISIT/PHONE CALL (estimated time window)	WHAT WILL HAPPEN?
Screening Visit (~45 minutes)	Review consent form and obtain consent Complete questionnaire, obtain diabetes history
Day of Discharge (~1 hour)	Complete FreeStyle Libre 2 CGM education Attach FreeStyle Libre 2 CGM sensor to your arm
Within 1-3 weeks from discharge Phone Call (~30 minutes)	Questions regarding use of FreeStyle Libre 2 CGM Current diabetes regimen Adverse Events Reminder to take FreeStyle Libre 2 CGM sensor prescription to pharmacy to be filled
1 & 3 Month Phone Call (~45 minutes) [+/- 5 days]	Questions regarding use of FreeStyle Libre 2 CGM Current diabetes regimen Complete questionnaire Adverse Events
6 Month Phone Call (~15 minutes) [+/- 10 days]	Questions regarding use of FreeStyle Libre 2 CGM Barriers to FreeStyle Libre 2 CGM use

D3 Visit 1a: During Hospital Stay

Study team member will meet with participant, review informed consent form and obtain written consent. Study team member will obtain the following information from patient or medical record after consent is obtained:

1. Most recent A1c

- 2. Height/Weight; calculate body mass index (BMI)
- 3. Year of diagnosis with diabetes
- 4. Type of diabetes
- 5. Has patient been admitted to the hospital or emergency department in the past 3 months for a diabetes related problem
- 6. Home diabetes regimen
- 7. Hospital diabetes regimen
- 8. Hospital discharge treatment regimen
- 9. Participant's reason/goal for using FreeStyle Libre 2 CGM
- 10. Does participant have frequent hypoglycemia or hypoglycemia unawareness
- 11. Complete "Diabetes Self-Management Questionnaire"

D4 Visit 1b: Day of Hospital Discharge:

On the day of participant's discharge from the hospital, one of the diabetes educators will complete the following with the participant:

- 1. Teach participant how to set up the FreeStyle Libre 2 CGM
- 2. Teach participant how to attach the FreeStyle Libre 2 CGM sensor to the upper arm
- 3. Teach participant how to measure blood glucose with FreeStyle Libre 2 CGM reader or personal smart phone
- 4. Assist participant download the free FreeStyle Libre 2 app from the app store on smart phone
- 5. Teach participant how to trouble shoot the FreeStyle Libre 2 CGM system
- 6. Provide participant with a handout for FreeStyle Libre 2 CGM system

The study physicians or nurse practitioners will provide the participant with a written prescription for three months of the FreeStyle Libre 2 CGM sensors to be filled by participant at their local pharmacy.

D5 Follow Up Telephone Calls

Within 1-3 Weeks after Discharge:

The study team will contact the participant by telephone to obtain the following information:

- 1. Is the participant still utilizing the FreeStyle Libre 2 CGM? If not, why was it stopped?
- 2. What barriers (such as discomfort, behavior modifications, lifestyle changes, diet changes) did the participant have with the FreeStyle Libre 2 CGM to limit use?
- 3. How satisfied with the FreeStyle Libre 2 CGM is the participant?
- 4. Has the participant been admitted to the hospital or been in the emergency department for a diabetes related problem since discharge?
- 5. Has the participant seen their outpatient diabetes provider since discharge?
- 6. What is the participant's current diabetes treatment regimen?

7. The study team will contact the participant to remind them to fill the prescription for a new FreeStyle Libre 2 CGM sensor with local pharmacy.

One Month after Discharge (+/- 5 days):

The study team will contact the participant by telephone to obtain the following information:

1. Is the participant still utilizing the FreeStyle Libre 2 CGM? If not, why was it stopped?
2. What is the average blood glucose for the past 30 days?
3. What barriers (such as discomfort, behavior modifications, lifestyle changes, diet changes) did the participant have with the FreeStyle Libre 2 CGM to limit use?
4. How satisfied with the FreeStyle Libre 2 CGM is the participant?
5. Has the participant been admitted to the hospital or been in the emergency department for a diabetes related problem since discharge?
6. Has the participant seen their outpatient diabetes provider since discharge?
7. What is the participant's current diabetes treatment regimen?
8. Administer the Diabetes Self-Management Questionnaire

Three Months after Discharge (+/- 5 days):

The study team will contact the participant by telephone to obtain the following information:

1. Is the participant still utilizing the FreeStyle Libre 2 CGM? If not, why was it stopped?
2. What is the average blood glucose for the past 30 days?
3. What barriers (such as discomfort, behavior modifications, lifestyle changes, diet changes) did the participant have with the FreeStyle Libre 2 CGM to limit use?
4. How satisfied with the FreeStyle Libre 2 CGM is the participant?
5. Has the participant been admitted to the hospital or been in the emergency department for a diabetes related problem since discharge?
6. Has the participant seen their outpatient diabetes provider since discharge?
7. What is the participant's current diabetes treatment regimen?
8. Administer the Diabetes Self-Management Questionnaire

Six Months after Discharge (+/- 10 days):

The study team will contact the participant by telephone to obtain the following information:

1. Is the participant still utilizing the FreeStyle Libre 2 CGM? If not, why was it stopped?

2. What barriers (such as discomfort, behavior modifications, lifestyle changes, diet changes) did the participant have with the FreeStyle Libre 2 CGM to limit use?

E Safety Monitoring

E1 Safety and Compliance Monitoring

The study team will meet every other week to review the status of the study, progress of recruitment, and adverse events. The study team will communicate directly with one another in between scheduled study team meetings if an unexpected adverse event occurs.

E2 Medical Monitoring

The study team will monitor patients throughout their participation in the study. Any adverse event or unexpected adverse event will be brought to the principal investigator within 24 hours of study team notification of event.

F Statistical Plan

F1 Sample Size Determination and Power

One hundred patients will be recruited for the study with the anticipation that 50% will agree to participate in the study.

F2 Statistical Methods

Statistical methods will include descriptive statistics (means, SD, median, IQR) and pre-test/post-test ANOVA for the questionnaire.

G References

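### B1's three feasibility thresholds are not tied to consistent counting bases, so meeting or missing them can turn on who is counted

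*Combined protocol and SAP*

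**What the plan says.** All references are to the combined protocol and SAP.

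- **Criterion 1 (B1 Primary Aim).** At least 20% of "patients with diabetes referred for diabetes education meet inclusion criteria to participate". Sections 2.c and D1, however, draw candidates from "patients referred to the diabetes service or diabetes education service". No number of referrals is given anywhere.
- **Criterion 2 (B1).** 75% agree. The sentence does not name the base; eligible patients is the natural reading. Eligibility itself contains willingness: inclusion 4 is "Able and willing to sign informed consent form", inclusion 6 requires readiness to pay for sensors after discharge, and exclusion 7 is "Unwilling to participate in the study".
- **Sample size.** C2 recruits 100 eligible adults. F1 also recruits 100, but expects half of them to agree. F1 gives no other figure.
- **Criterion 3 (B1).** "From those who participate, at least 50% continue using the CGM at 3 months". Use is measured at the telephone call headed "Three Months after Discharge (+/- 5 days)", by the question "Is the participant still utilizing the FreeStyle Libre 2 CGM? If not, why was it stopped?". Section 2.e says "Participants may be withdrawn if certain situations arise", without saying whether withdrawn people are still asked.
- **Analysis (F2).** Descriptive summaries for continuous data and a pre/post ANOVA for the questionnaire. F2 names no proportion, no interval and no rule for missing answers.

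**The concern.** Feasibility is defined wholly by three proportions against three thresholds, so their numerators and denominators are the primary analysis. Four of these counts are open or inconsistent: the pool for criterion 1, whether refusers are eligible, who the 100 are, and what an unanswered 3-month call means. Each can be settled after the data are seen, and near a threshold that choice decides the result. Counting refusers as ineligible makes agreement look better and eligibility worse. Dropping unreached people at 3 months can make continuation look better; counting them as stopped makes the criterion partly a measure of call completion.

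**Working it through.** **(a) Pool for criterion 1.** B1's denominator is education referrals. The group screened under 2.c and D1 also includes people referred only to the diabetes service. If they enter the numerator but not the denominator, the ratio is not a proportion of one population. The size of this effect cannot be computed, because the plan gives no referral counts.

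**(b) Willingness inside eligibility.** Assumed counts, for illustration only: 500 referred, 120 meeting every criterion apart from willingness, 90 agreeing.

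| Count | Criterion 1 | Criterion 2 |
|---|---|---|
| Willingness outside eligibility | 120/500 = 24.0% (met) | 90/120 = 75.0% (met) |
| Inclusion 4 and exclusion 7 read literally | 90/500 = 18.0% (not met) | 90/90 = 100% |

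The same patients give the opposite result on criterion 1.

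**(c) Who the 100 are.** F1 gives no alpha, power, precision or dropout, so the 100 cannot be reproduced. What follows from the stated figures is:

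- 100 approached at F1's rate: 100 × 0.50 = 50 participants.
- 100 approached at B1's rate: 100 × 0.75 = 75 participants.
- 100 participants, as C2 can be read: 100/0.50 = 200 approached, or 100/0.75 = 133.3, so 134.

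If true agreement were the 50% that F1 expects, the chance of at least 75 agreeing out of 100 is P(Bin(100, 0.50) ≥ 75) = 0.0000003. F1's expectation therefore amounts to expecting criterion 2 to fail.

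**(d) Missing 3-month answers.** The plan states no loss rate, so the losses here are assumptions. Let U be the number of reported users, N = 100, with 20 unanswered.

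- Over all participants, missing counted as stopped: met if U/100 ≥ 50%, so U ≥ 50.
- Among those reached: met if U/80 ≥ 50%, so U ≥ 40.
- Over all participants, missing counted as continuing: met if (U + 20)/100 ≥ 50%, so U ≥ 30.

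Hence U from 40 to 49 fails on the first count and passes on the second. For U = 44 the three rates are 44%, 44/80 = 55% and 64%.

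With missing counted as stopped, the share of users needed among those reached is 50/(100 − m):

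| Unanswered (m) | Share needed among those reached | Chance of meeting 50% if true continuation is 60% and loss is unrelated to use |
|---|---|---|
| 0 | 50.0% | 0.983 |
| 5 | 52.6% | 0.941 |
| 10 | 55.6% | 0.834 |
| 15 | 58.8% | 0.632 |
| 20 | 62.5% | 0.369 |

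The last column is P(Bin(100 − m, 0.60) ≥ 50). The contacted-only rate can err the other way: if true continuation is 45% and all 20 unreached people have stopped, it is 45/80 = 56.25%.

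**Precision.** With no loss, a result exactly at 50% has an exact (Clopper-Pearson) 95% CI of 39.8% to 60.2% for 50/100, and 35.5% to 64.5% for 25/50. The ambiguity in (c) therefore also affects the precision of criterion 3.

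**The case against.** This is a small single-arm feasibility study with descriptive aims, and much of the above is loose wording. B1 separates meeting the criteria from agreeing, and F1 expects half to agree, so the authors evidently mean refusers to be counted. A reader might infer from inclusion 4 and exclusion 7 that the study will report 100% agreement; F1 does not support that. What stands is that the eligibility list, applied as written, produces that result, and nothing tells the person keeping the screening log otherwise.

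A reader might also infer that the plan gives conflicting numbers for criterion 1. It gives no number there; only the source populations differ. Nor does criterion 3 lack a denominator: B1 supplies one, and the gap is in classifying people with no answer.

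The loss counts are assumed. The background section's outpatient studies report completion of 12 of 17, 48.9%, and 55 of 60, but their settings and definitions differ, so they show that loss is foreseeable without estimating it here. B1 also does not say that continuation means reported continuation; that is the literal consequence of having only a telephone answer.

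Finally, a reader might call the absence of a confidence interval an error. F2's list is not worded as complete, and an interval can be computed from any reported n/N. Planning one is good practice, and its absence does not invalidate the analysis.

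**Conclusion.** The concern holds as a problem of inconsistent counting bases. Three parts rest on the text alone: the referral pool differs between B1 and 2.c/D1; willingness is placed inside eligibility while B1 treats agreement as a separate step; and C2, F1 and B1 cannot all hold, since 100 is either participants or people approached and F1's 50% would miss B1's 75%. The fourth part, no rule for a missing 3-month answer, is also plain from the text, but its size depends on assumed loss: with 20 of 100 unanswered, the result on criterion 3 depends on the counting rule for 40 to 49 reported users if the choice is between all participants and those reached.

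The documents do not support the stronger inference that the 3-month rate will be biased by a known amount or in a known direction. That depends on how many calls are missed and whether those people are still using the device. The study remains interpretable; what needs repair is that its primary conclusion should not rest on counting choices left open.

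**What to change.** In B1, C2, F1 and F2:

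1. **The 100.** State whether they are patients approached or participants, and reconcile F1's 50% with B1's 75%.
2. **Criterion 1.** Name one referral population and use it for both numerator and denominator.
3. **Criterion 2.** Count consented patients over approached patients who meet every criterion other than willingness to consent (inclusion 4, exclusion 7). State whether unwillingness to buy sensors (inclusion 6) counts under criterion 1 or 2.
4. **Criterion 3.** Use all consented participants. Say how a person who consented at Visit 1a but never had a sensor attached at Visit 1b is counted. Take a missing 3-month answer, including one missing after withdrawal under 2.e, as not continuing for the primary result. Show the contacted-only and missing-as-continuing rates as sensitivity analyses.
5. **Reporting.** Give each criterion as n/N with an exact 95% CI beside its threshold.

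The cost is a screening log, a few sentences and a little more analysis. The primary 3-month rate will be conservative when calls are missed; the table under (d) shows how quickly that matters. At N = 100 the range between the two extreme counts widens by one percentage point per missing answer. The contacted-only rate equals the true rate only if unreached people resemble those reached.

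### Secondary aim 2 is to assess an effect on time in range, but no planned contact records time in range and no baseline value is planned

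*Combined protocol and SAP*

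**What the plan says.** **The aim.** B2 item 2 reads "To assess the effect of CGM initiation at hospital discharge on diabetes outcomes: Time in range", followed by "health utilization (clinic visits, ED visits, hospitalization" and self-efficacy. Time in range is the first outcome named. Its only other mention is in the background, about a cited study.

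**The design.** C1: "This study will be an interventional, single-arm, open-label, prospective design". Section 2.b item 4 excludes people who "Have utilized CGM in the past". In D2 the day-of-discharge row is where the study staff "Attach FreeStyle Libre 2 CGM sensor to your arm", and no earlier sensor wear is described.

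**Glycemic data collected.** D3 (Visit 1a) item 1 is "Most recent A1c", obtained from the patient or the medical record. In D5, item 2 of both the 1-month and the 3-month call is "What is the average blood glucose for the past 30 days". The 1-3 week and 6-month calls ask for no glucose value.

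**Analysis.** F2 offers descriptive statistics in general and a pre/post ANOVA for the questionnaire. It does not mention time in range.

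**The concern.** An outcome named in an aim should be traceable to a contact at which it is recorded, a definition, and an analysis. Time in range has none of the three specifically: no item records it, no glucose limits are given, and F2 does not name it. A team that follows the plan exactly reaches the end with no data on the first-named outcome of secondary aim 2. Because no transfer of device data to the study team is described, values not asked for during the calls may not be recoverable later.

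The second difficulty is the word effect. With one arm, an effect has to be read from a before/after contrast in the same people, and the plan provides no before value. Adding a question to the calls would supply data, but would not by itself supply that contrast.

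**Working it through.** The documents state no figure for time in range, so there is nothing to reproduce. The check is a count, two comparisons of sections, and one illustrative calculation.

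**1. Count of numbered items in D3 to D5.**

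| Contact | Items | Time in range | Other glycemic item |
|---|---|---|---|
| Visit 1a (D3) | 11 | 0 | A1c |
| Visit 1b (D4) | 6 | 0 | none |
| 1-3 week call (D5) | 7 | 0 | none |
| 1-month call (D5) | 8 | 0 | 30-day average |
| 3-month call (D5) | 8 | 0 | 30-day average |
| 6-month call (D5) | 2 | 0 | none |

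Total: 11 + 6 + 7 + 8 + 8 + 2 = 42, with time in range in 0. The six Visit 1b items are teaching, app help or a handout, and item 7 of the 1-3 week call is a reminder. Without these seven the denominator is 42 − 7 = 35, and the count is still 0. Time in range is also in 0 of the 5 rows of the D2 table. The general D2 entry on questions about CGM use does not fill the gap, because D5 lists those questions one by one and none is time in range.

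**2. Can the average glucose stand in for it?** The average is probably a CGM figure, since D4 item 3 uses the same term for a sensor reading ("Teach participant how to measure blood glucose with FreeStyle Libre 2 CGM reader or personal smart phone"), though D5 does not say so. Even so, a mean does not fix the share of readings within limits. As an illustration, assume limits of 70 to 180 mg/dL and normally distributed glucose with mean m and SD = CV × m; the documents give none of these. Then time in range = Φ((180 − m)/SD) − Φ((70 − m)/SD).

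- m = 150, CV 20% (SD 30): Φ(1.00) − Φ(−2.67) = 83.8%.
- m = 150, CV 50% (SD 75): Φ(0.40) − Φ(−1.07) = 51.2%.
- m = 180, CV 20% (SD 36): 49.9%.
- m = 180, CV 50% (SD 90): 38.9%.

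At a mean of 150 mg/dL, time in range differs by 83.8 − 51.2 = 32.6 percentage points with CV alone. The average cannot be converted.

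**3. Is there a baseline?** Visit 1a records an A1c but neither an average glucose nor time in range. The average is recorded only at follow-up and A1c only at baseline, so no glycemic measure has both values. For CGM-derived time in range, prior users are excluded and the first sensor is attached on the day of discharge, so a value from before initiation cannot exist. There is also no comparison group.

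**4. What a 30-day look-back would cover.** Take 1 month as 30 days (an assumption). With the ±5-day window the 1-month call falls on days 25 to 35. On day 25 a 30-day look-back would start 30 − 25 = 5 days before the sensor was attached, so at most 25 days of data exist. The 3-month call falls on days 85 to 95, and its look-back starts on days 55 to 65, well after attachment.

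**5. Who would contribute at 3 months.** B1 sets the threshold for continued use at 50%. If 100 people take part and exactly half continue, 100 × 0.5 = 50 would have a value. If F1 means that only half of the 100 agree, 50 × 0.5 = 25 would.

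**The case against.** The strongest reply is that this is one of three outcomes in the second secondary aim of a feasibility study, and that F2 promises only descriptive statistics outside the questionnaire. On that view nobody planned an inferential analysis of time in range, and the complaint about effect is a matter of wording. This stands in part: description is all that F2 offers, which is why rewording the aim is enough on that side. It does not supply the missing data, since nothing can be described if nothing is recorded.

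A reader might also infer more than the documents support.

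- *That no value of any kind from before CGM could exist.* This holds only for CGM-derived time in range. B2 does not say that the figure must come from CGM, and a share of inpatient or fingerstick readings in range could in principle be formed. The protocol plans none, and it would not be the same measure.
- *That the average lacks a baseline because A1c is not repeated.* These are separate facts. The average lacks a baseline because Visit 1a records no average.
- *That all of aim 2 fails.* It does not. The self-management questionnaire is given at Visit 1a, 1 month and 3 months. Diabetes-related admission or ED attendance is asked at Visit 1a and at three calls, and diabetes-provider visits at three calls. The baseline admission/ED item covers 3 months and the 3-month call asks about the time since discharge, so a roughly matched comparison of that item is available.

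The wording of the utilization outcomes is a separate and minor matter.

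**Conclusion.** The concern holds, limited to time in range. As written, the plan yields no data on the first-named outcome of secondary aim 2: 0 of 42 numbered items, 0 of 35 on the stricter count, and 0 of 5 schedule rows. The average glucose at two calls cannot replace it. If the figure is added, it supports a description among people using the CGM, not an effect, because no baseline is planned, a CGM-derived one cannot exist, and the study has one arm.

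The count and the baseline argument rest only on the protocol text. The 32.6-point spread rests on assumed limits, a normal distribution and assumed CVs; it illustrates why the mean is not enough and does not estimate what this trial would see. The matter should be fixed, but it does not touch the primary feasibility aim.

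**What to change.** 1. Confirm that the study device displays time in range. The documents do not say, and the background notes that displays differ between devices.
2. If it does, add it to the 1- and 3-month calls already scheduled. Record the glucose limits, the source (reader or app), the wear during the period, and the same 30-day look-back as the average glucose question. Note when fewer than 30 days of sensor data exist. Record 'not available' for those not using the CGM.
3. Reword this part of B2 item 2 as: *To describe time in range during CGM use at 1 and 3 months among participants using the CGM.* Report it descriptively with N at each time, and state that continuing users are a selected group.
4. A value at the 1-3 week call is optional. If taken, label it an early on-device value, not a baseline.
5. If the figure cannot be obtained, remove time in range from the aim.
6. Minor: narrow the utilization wording in B2 to what D3 and D5 collect, namely diabetes-related admission or ED visit, and outpatient diabetes provider visit.

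The cost is a few extra questions on existing calls, a change of aim wording and no new visit. The downside is a weaker, descriptive claim in place of an effect.
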